#### *2.4.4.1.3 EDSS*

The observed value, change from baseline as well as percentage change from baseline will be presented descriptively. The change from baseline in EDSS will be analyzed using a mixed model for repeated measures (MMRM) (7)(8)(9) with baseline EDSS score, analysis group indicator (IAT and DAT), geographic region, study visit and study visit by analysis group interaction as covariates. The TOPAZ study baseline at study entry is considered as post-baseline for efficacy analysis. The comparison of the change from baseline in EDSS with the MMRM will include the change from baseline to each consecutive year which can be constructed using the linear contrasts of the estimated regression parameters. All post-baseline EDSS scores will be included in the MMRM; patients without any post-baseline scores will not be included. For this model, imputation will not be used.

Similar analysis for change of EDSS by alemtuzumab courses and for retreated population will be analyzed as well.

#### *2.4.4.1.4 MRI lesion count*

The observed lesion count and change from baseline will be presented descriptively by analysis groups.

The cumulative count of lesions will be compared between IAT and DAT groups through a repeated negative binomial regression adjusted for the long-term baseline count, analysis groups and geographic region. The comparison of proportion of patients with lesion at any time post-baseline between IAT and DAT group will be analyzed using repeated measure generalized estimating equation (GEE) with logistic link. Covariates will include long-term baseline lesion count, geographic region, and analysis groups.

Similar analysis for MRI lesion count by alemtuzumab courses and for retreated population will be analyzed as well.

#### **2.4.4.1.5 MRI volume and BPF**

The observed value, change from baseline as well as percentage change from baseline will be presented descriptively.

The percent change in lesion volume / BPF from year to year and the percent change from long-term baseline will be calculated by analysis groups. To compare between IAT and DAT patients, the percent change from baseline in MRI lesion volume will be analyzed yearly using the ranked analysis of covariance (ANCOVA) model with adjustment for baseline lesion volume, analysis groups (IAT and DAT) and geographic region.

Similar analysis for MRI volume by alemtuzumab courses and for retreated population will be analyzed as well.

#### **2.4.4.2 Multiplicity issues**

Not applicable.

#### **2.4.5 Analyses of safety data**

The summary of safety results will be presented in overall group and by subgroups (IAT vs DAT).

Only data collected in TOPAZ study will be used for analysis in addition of baseline information from previous studies.

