# 1 FLOW CHARTS

## 1.1 GRAPHICAL STUDY DESIGN

- ★ Only for patients treated with alemtuzumab: monthly laboratory safety variables collection for 48 months after last infusion
  - For patients who received alemtuzumab in CAMMS03409 study less than 48 months before entering in LPS13649 study, and
  - For patients receiving retreatment with alemtuzumab during the LPS13649 study

\* After completion of 5 years of the first patient inclusion, the next scheduled visit for any patient will be performed as EOS visit.

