## **7 SELECTION OF PATIENTS**

### **7.1 INCLUSION CRITERIA**

- I 01. Patient has completed at least 48 months of the Extension Study CAMMS03409.
- I 02. Signed written informed consent form (ICF).

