## 9.5.2 Laboratory safety variables

### 9.5.2.1 *Patients exposed to alemtuzumab within 48 months prior to inclusion in this study*

- The following parameters must be obtained at monthly intervals until 48 months after the last infusion of alemtuzumab administered in the study CAMMS03409:
  - CBC with differential (including platelet count).
  - Serum creatinine.
  - Urinalysis (minimally including determination of urine protein and red blood cells) with microscopy.
- TSH must be obtained every 3 months until 48 months after the last infusion of alemtuzumab administered in the study CAMMS03409.
- For women, a Human Papilloma Virus (HPV) screening must be performed as follows:
  - For women within 48 months follow-up at time of study transition from CAMMS03409 to TOPAZ, the date of the last alemtuzumab infusion administered in the study CAMMS03409 must be checked, and then an HPV screening performed approximately 1 year after the last infusion of alemtuzumab, and then every 12 months until 48 months safety FU is completed.

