### 1.4 STUDY PLAN

The whole clinical trial of alemtuzumab consists of three study periods:

CAMMS223/323/324 prior studies (2 years): to compare the efficacy and safety of alemtuzumab to subcutaneous (SC) interferon beta-1a (IFNB-1a, Rebif) in treatment-naïve patients with relapsing-remitting multiple sclerosis (RRMS) who had recent MS disease activity as demonstrated by clinical relapses.

CAMMS03409 extension study (at least 4 years): to examine the long-term efficacy and safety of alemtuzumab in MS patients who received alemtuzumab during prior studies CAMMS223/323/324 and the efficacy and safety of 2 fixed annual alemtuzumab courses in patients who previously received SC IFNB-1a during prior studies.

LPS13649 (TOPAZ) extension study (5 years): to evaluate the long-term safety, efficacy and Quality of life (QoL) of alemtuzumab in patients who have completed at least 48 months of the extension study CAMMS03409.

- ★ Only for patients treated with alemtuzumab: monthly laboratory safety variables collection for 48 months after last infusion
  - For patients who received alemtuzumab in CAMMS03409 study less than 48 months before entering in LPS13649 study, and
  - For patients receiving retreatment with alemtuzumab during the LPS13649 study
- \* After completion of 5 years of the first patient inclusion, the next scheduled visit for any patient will be performed as EOS visit.

Scheduled visits for safety and efficacy assessments will be performed every six months. AEs and concomitant medications will be monitored continuously. Quality of life, pharmaco-economic data and brain imaging will be collected every twelve months (Table 1).

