### ***Analysis of adverse events of special interest (AESI)***

- All treatment-emergent adverse events of special interest by primary SOC, HLG, HLT, and PT, showing the number (%) of patients sorted by the internationally agreed SOC order. The other levels (HLG, HLT, PT) will be presented in alphabetical order
- All treatment-emergent adverse events of special interest by primary SOC and PT, showing the number (%) of patients with at least 1 treatment-emergent adverse event, sorted by the internationally agreed SOC order and by decreasing incidence of PTs within each SOC. This sorting order will be applied to all other tables, unless otherwise specified
- All treatment emergent adverse events of special interest by PT, showing the number (%) of patients, sorted by decreasing incidence of PT
- The event rate per patient-year (the number of events in question divided by total treatment exposure in patient years) for non-temporary AESI(s) will be provided by SOC and PT
- The frequency of treatment-emergent adverse events over time will be provided for the non-temporary treatment-emergent AESIs, where the time intervals will be defined as: <2 courses, 2 – 4 courses, 4 – 6 courses, 6 – 8 courses, etc. In each time interval, the denominator for calculation of percentage will be the number of patients who entered the time interval and the numerator will be the number of patients with at least 1 treatment emergent AESI occurring in this time interval. Note that only the first event will be counted and all recurrent events will not be included
- For retreated population, the frequency of treatment-emergent temporary adverse events over time will be provided for the temporally associated AESIs (pulmonary alveolar hemorrhage, myocardial ischemia, myocardial infarction, stroke, cervicocephalic arterial dissection), where the time intervals will be defined as: during alemtuzumab infusion day 1, during alemtuzumab infusion day 2, during alemtuzumab infusion day 3, 1 day after alemtuzumab infusion, 2 days after alemtuzumab infusion and 3 days after alemtuzumab infusion. In each time interval, the denominator for calculation of percentage will be the number of patients who entered the time interval and the numerator will be the number of patients with at least 1 treatment emergent AESI occurring in this time interval. Note that only the first event will be counted and all recurrent events will not be included

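### AESI tables pool follow-up with and without scheduled laboratory tests, so differences between IAT and DAT or between course bands partly reflect testing intensity

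*SAP*

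**What the plan says.** **Who is tested.** Protocol 1.1 limits scheduled laboratory monitoring: "Only for patients treated with alemtuzumab: monthly laboratory safety variables collection for 48 months after last infusion". SAP 1.4 names two groups. One is defined by treatment before entry: "For patients who received alemtuzumab in CAMMS03409 study less than 48 months before entering in LPS13649 study, and". The other is defined by treatment after entry: "For patients receiving retreatment with alemtuzumab during the LPS13649 study". CBC, creatinine and urinalysis are monthly. Thyroid testing is less frequent: "TSH must be obtained every 3 months until 48 months after the last infusion of alemtuzumab administered in the study CAMMS03409" (Protocol 9.5.2.1). Liver function tests (LFT) are monthly after re-treatment. For patients treated before entry, Protocol 9.5.2.1 does not list LFT, whereas Protocol 10.1.6.2 and SAP 2.1.4.3 do.

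**Who is not.** The 6- and 12-monthly visits that all patients attend (Protocol 1.2.1, 10.1.2, 10.1.3) include adverse event collection and vital signs but no safety blood or urine test.

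**How results are tabulated.** SAP 2.4.5.3 restricts the laboratory tables to the retreated and 48-month follow-up populations. Adverse event and AESI percentages use the whole safety population as denominator (SAP 2.4.5.1), and SAP 2.4.5 sets the layout: "The summary of safety results will be presented in overall group and by subgroups (IAT vs DAT". AESI rates per patient-year are given by SOC and PT. There is also a table by course band: "The frequency of treatment-emergent adverse events over time will be provided for the non-temporary treatment-emergent AESIs". No AESI table separates time inside the 48-month window from time beyond it.

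**The concern.** Several AESIs are found wholly or largely through these tests. ALT increase is defined by a laboratory value (Protocol Table 2). Thyroid disorders, ITP and other cytopenias, and nephropathies are what the TSH, blood count, creatinine and urinalysis schedule looks for. Protocol Appendix C puts autoimmune thyroid disorders at 36%, ITP at 2% and nephropathies at 0.3%, so the commonest listed autoimmune event is among those affected.

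Safety is the primary endpoint. If one group spends more of its TOPAZ time under scheduled testing, it will show more of these events even when true risk is the same. A low count in patients long past their last infusion could be read as fading risk. A higher count in recently treated patients could be read as harm from later or additional courses. The pooled tables give the reader no means of telling these apart.

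**Working it through.** The documents contain no sample size, power or expected rate for this point, so there is no plan figure to reproduce.

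**Inputs**
- Core study length: "CAMMS223/323/324 prior studies (2 years" (SAP 1.4), so core months 0 to 24.
- Minimum extension time: "Patient has completed at least 48 months of the Extension Study CAMMS03409" (Protocol 7.1). Protocol section 4 gives a maximum of 60 months.
- Gap before TOPAZ D1: up to 3 months, or 6 in the US (Protocol 10.1.1).
- Test window: 48 months after last infusion.
- DAT: 2 fixed annual courses in the extension (SAP 1.4), taken here as extension months 0 and 12.
- TOPAZ follow-up: 60 months. This is about the longest possible, because the study closes 5 years (plus a 6-month window) after the first patient enters.

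**Step 1: test months left at D1** = max(0, month of last infusion + 48 − month of D1), counted from core baseline.
- IAT dosed only in the core study, latest possible infusion at month 24: 24 + 48 = 72. The earliest D1 is 24 + 48 = 72, so 0 months remain in every scenario.
- Two-course DAT, last infusion at month 24 + 12 = 36: window closes at 36 + 48 = 84. D1 at month 72, 78 or 84 (extension month 48, 54 or 60, no gap) leaves 12, 6 or 0 months, which is 20%, 10% or 0% of 60. A 3-month gap after a 48-month extension reduces 12 to 9.
- Any patient, IAT or DAT, re-treated in TOPAZ by month 12: 48 of 60 months, or 80%.

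**Step 2: spurious excess for two-course patients under equal, constant true risk.** Let m be the tested share of follow-up and s the share of events found without scheduled tests. The documents do not give s, so 0.25, 0.50 and 0.75 are assumed. Scheduled tests are taken to find every event in tested time.
- Detected fraction = m + (1 − m)s; for two-course IAT, m = 0 and this equals s.
- Excess as a share of detected DAT events = m(1 − s) / [m + (1 − m)s].

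| DAT entry | m | s = 0.25 | s = 0.50 | s = 0.75 |
|---|---|---|---|---|
| Month 48 | 0.20 | 0.150/0.400 = 38% | 0.100/0.600 = 17% | 0.050/0.800 = 6% |
| Month 54 | 0.10 | 0.075/0.325 = 23% | 0.050/0.550 = 9% | 0.025/0.775 = 3% |
| Month 60 | 0 | 0% | 0% | 0% |

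As DAT/IAT ratios, month-48 entry gives 0.400/0.25 = 1.60, 0.600/0.50 = 1.20 and 0.800/0.75 = 1.07.

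**Step 3: whole groups.** The planned tables compare all IAT with all DAT. As an illustration, suppose a fraction r of IAT is re-treated early in TOPAZ (80% tested), the rest of IAT is untested, and all DAT have two courses and month-48 entry (20% tested). Tested shares are equal when 0.80r = 0.20, so r = 0.25. Above that, IAT is the more heavily tested group. The documents do not give r or its DAT counterpart.

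**The case against.** The strongest reply has five parts.

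1. *The direction is unknown.* A reader might infer that DAT must show more laboratory-detected AESIs than IAT. That holds only between two-course patients. IAT patients could be re-treated as needed in CAMMS03409 or in TOPAZ and are then tested too, so the net difference could go either way (step 3). This stands.
2. *The laboratory tables already guard against this.* They are restricted to monitored populations, and PCSA denominators count only patients assessed (SAP 2.4.5). This is true of those tables, but the AESI tables have no such restriction.
3. *The size is easily overstated.* A reader might set early re-treated patients against two-course IAT patients and obtain ratios from 1.27 to 3.4, but no planned table makes that contrast. The 2-4 course band holds two-course IAT, two-course DAT and three-course patients together, and only percentages, not rates, are planned by band. Nor is the share of DAT events falling in tested time (0.2/0.8 = 25% to 0.2/0.4 = 50% at month-48 entry) the bias, since many of those events would be found anyway. This stands.
4. *Untested does not mean unobserved.* Adverse events are collected at every visit, and investigators may order tests at any time. This stands: what is absent is scheduled laboratory testing.
5. *Safety is descriptive.* SAP 2.4.5 plans no systematic testing, and IAT versus DAT is the main comparison for efficacy only. That lowers the stakes but does not remove the problem, because descriptive columns placed side by side are still read as a comparison.

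**Conclusion.** The point holds as a limit on interpretation. For laboratory-detectable AESIs, the pooled percentages and rates mix tested and untested time, and the mix differs between the groups displayed.

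For two-course patients, the spurious excess is 6-38% of detected DAT events at month-48 entry, 3-23% at month 54 and none at month 60. This rests on equal and constant true risk, no entry gap, a 60-month follow-up, a second DAT course at extension month 12 and an assumed s of 25-75%. An entry gap lowers the tested share; a shorter follow-up raises it wherever test months remain.

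For IAT against DAT as whole groups, neither size nor direction can be derived. Testing also follows time since infusion, which may itself change risk, so any observed difference can be attributed to surveillance only in part.

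**What to change.** In SAP 2.4.5.1, for thyroid disorders, ITP and other cytopenias, nephropathies and ALT increase, add a descriptive split of TOPAZ events and TOPAZ person-time into within and beyond 48 months of the last infusion. Update the last-infusion date at each new course. Show the split overall, by IAT/DAT and by course band.

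Reconcile the LFT schedule in Protocol 9.5.2.1 with Protocol 10.1.6.2 and SAP 2.1.4.3, and define the ALT stratum by the LFT schedule actually applied.

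Footnote the pooled tables with two statements. First, the extent of scheduled testing differed between groups. Second, the within-48-month stratum contains no IAT patients dosed only in the core study, so it sets IAT patients selected by re-treatment beside DAT patients and must not be read as a randomised-like comparison.

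The change uses infusion dates already collected and needs no new tests. The cost is programming and smaller strata. Confounding by time since infusion and by selection for re-treatment remains.

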#### **General common rules**

All safety analyses will be performed on the safety population as defined in [Section 2.3.1.1](#), unless otherwise specified, using the following common rules:

- The baseline value is defined as the available value assessed on or prior to the V01 Selection visit, unless otherwise specified. If laboratory, vital sign and physical examinations were performed in CAMMS03409 study within the pre-specified time-windows, then the last assessment within the time-window can be considered as baseline when the corresponding V01 assessments are missing.
- The potentially clinically significant abnormality (PCSA) values are defined as abnormal values considered medically important by the Sponsor according to predefined criteria/thresholds based on literature review and defined by the Sponsor for clinical laboratory tests and vital signs (PCSA version dated May 2014 [[Appendix A](#)])
- PCSA criteria will determine which patients had at least 1 PCSA during the treatment-emergent adverse event period, taking into account all evaluations performed during the treatment-emergent adverse event period, including nonscheduled or repeated evaluations.

The number of all such patients will be the numerator for the on-treatment PCSA percentage

- The treatment-emergent PCSA denominator by group for a given parameter will be based on the number of patients assessed for that given parameter in the treatment-emergent adverse event period in overall group and by subgroups (IAT vs DAT) on the safety population.
- For quantitative safety parameters based on central laboratory/reading measurements, descriptive statistics will be used to summarize results and change from baseline values by visit and analysis group.
- The analysis of the safety variables will be essentially descriptive and no systematic testing is planned.

#### **2.4.5.1 Analyses of adverse events**

##### ***Generalities***

All the reported AE will be considered as treatment emergent adverse event (TEAE).

Adverse event incidence tables will present by SOC, HLGT, HLT, and PT, sorted in alphabetical order in overall group and by subgroups (IAT vs DAT), the number (n) and percentage (%) of patients experiencing an adverse event. Multiple occurrences of the same event in the same patient will be counted only once in the tables. The denominator for computation of percentages is the safety population in overall group and by subgroups (IAT vs DAT).

Sorting within tables ensures the same presentation for the set of all adverse events within the observation period. For that purpose, the table of all treatment-emergent adverse events presented by SOC and PT sorted by the internationally agreed SOC order and decreasing frequency of PTs in overall group within SOCs will define the presentation order for all other tables unless otherwise specified.

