### 10.1 VISIT SCHEDULE

#### 10.1.1 Visit 1: selection (D1)

This visit must be conducted within 3 months (6 months for US, see [Appendix D](#)) after completion of the Extension Study CAMMS03409. When possible, Visit 1 will be performed at the same time as the last visit of the Extension Study CAMMS03409.

Prior to any assessments, information for the patient regarding the aims and methods of the study, its constraints and risks will be reviewed with the patient and a written summary in the form of an informed consent will be given to the patient. The patient must sign the informed consent before continuing the visit. The patient will keep the same patient number as used in the Extension Study CAMMS03409.

The following items will be checked/performed and recorded:

- Informed consent signature.
- Eligibility by review of Inclusion/Exclusion criteria ([Section 7](#)).
- Date of the last infusion of alemtuzumab.
  - If the treatment was administered within the previous 48 months, the patient must be followed-up as described in [Section 10.1.6.2](#).
- Safety assessments ([Section 9.5](#)).
  - Collection of AEs still ongoing at the end of the Extension Study CAMMS03409.
  - Collection of the AE that occurred between the final visit of the CAMMS03409 study and Visit 1.
  - Collection of laboratory results, if any, performed between the final visit of the CAMMS03409 study and Visit 1.
  - Vital signs and physical examination (only if not performed and collected in the previous 3 months).
- Efficacy assessments ([Section 9.6](#)).
  - MS relapse verification.
  - EDSS (only if not performed and collected in the previous 3 months).
  - Brain imaging to include: G-MRI, MRI-T1 and MRI-T2 T1 pre- and post-Gadolinium (Gd), T2/PD, FLAIR and T1 sagittal sequences (only if not performed and collected in the previous 6 months).

- Health questionnaires: SF-36, FAMS and EQ-5D (only if not performed in the previous 3 months).
- Pharmacoeconomic assessment: modified HRUQ/HRPQ ([Section 9.7](#)) (only if not collected in the previous 3 months).
- Previous medication (from the end of the Extension Study CAMMS03409 to Visit 1 of LPS13649 study).
- Concomitant medication.

An appointment should be scheduled for next visit in 6 months ( $\pm 14$  days).

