#### **10.4.1.4 Events not to be considered as AEs/SAEs**

Medical conditions present at the initial trial visit (Visit1) that do not worsen in severity or frequency during the trial are defined as baseline medical conditions, and are not to be considered AEs. However, baseline medical conditions other than the disease under trial that worsen in severity or frequency during the trial should be recorded and reported as AEs.

In this protocol, symptoms and signs of exacerbation or worsening of the disease under trial will usually be captured in the context of efficacy assessment, and recorded on the relapse module of the eCRF. Therefore, symptoms, relapses or worsening of MS will not be considered as AEs nor captured on the AE module of the eCRF unless this event is considered possibly or probably related to the IMP (ie, worsening is not consistent with the anticipated natural progression of the disease) and/or the MS relapse meets the criteria for a serious AE (eg, requires hospitalization).

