#### **10.4.2 General guidelines for reporting adverse events**

- All AEs, regardless of seriousness or relationship to IMP, spanning from the signature of the informed consent form until the end of the study as defined by the protocol for that patient, are to be recorded on the corresponding page(s) or screen(s) of the CRF. At Visit 1 the ongoing AEs started during the Extension Study CAMMS03409, or occurred between the final visit of the CAMMS03409 study and Visit 1, are also to be recorded.
- Whenever possible, diagnosis or single syndrome should be reported instead of symptoms. The Study Investigator should specify the date of onset, intensity, action taken with respect to IMP, corrective treatment/therapy given, additional investigations performed, outcome, and his/her opinion as to whether there is a reasonable possibility that the AE was caused by the IMP or by the study procedure(s).
- The Study Investigator should take appropriate measures to follow all AEs until clinical recovery is complete and laboratory results have returned to normal, or until progression has been stabilized, or until death, in order to ensure the safety of the patients. This may imply that observations will continue beyond the last planned visit per protocol, and that additional investigations may be requested by the monitoring team up to as noticed by the Sponsor.
- When treatment is prematurely discontinued, the patient's observations will continue until the end of the study as defined by the protocol for that patient.
- Laboratory, vital signs or ECG abnormalities are to be recorded as AEs only if:
  - Symptomatic and/or
  - Requiring either corrective treatment or consultation, and/or
  - Leading to IMP discontinuation or modification of dosing, and/or
  - Fulfilling a seriousness criterion, and/or
  - Defined as an AESI.
- AEs/AESIs that are ongoing at the end of the patient's participation in CAMMS03409 should be followed during the LPS13649 study.

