| Event category | Reporting timeframe | Specific events in this category                                  | Case report form completion |  |                      |
|----------------|---------------------|---|-----------------------------|--|----------------------|
|                |                     |   | AE form                     | Safety complementary form a | Other specific forms |
|                |                     | Progressive Multifocal Leukoencephalopathy (PML)                  | Yes                         | Yes                                    | No                   |
|                |                     | Pneumonitis   | Yes                         | Yes                                    | No                   |
|                |                     | Temporally associated* pulmonary alveolar hemorrhage              | Yes                         | Yes                                    | No                   |
|                |                     | Temporally associated* myocardial ischemia, myocardial infarction | Yes                         | Yes                                    | No                   |
|                |                     | Temporally associated* stroke                                     | Yes                         | Yes                                    | No                   |
|                |                     | Temporally associated* cervicocephalic arterial dissection        | Yes                         | Yes                                    | No                   |
|                |                     | (* Temporally associated: 1 to 3 days after the last infusion)    |                             |  |                      |
|                |                     | Malignancy  | Yes                         | Yes                                    | No                   |

AE = adverse event; AESI = adverse event of special interest; GBM = Glomerular Basement Membrane; SAE = serious adverse event.

a If an SAE or an AESI ongoing from the CAMMS study is reported in TOPAZ study, the Safety Complementary Form need not be completed.

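### The SAP counts every reported AE as treatment-emergent, so the primary safety tables can mix events that began before TOPAZ with new ones

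*SAP*

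**What the plan says.** The rule is in SAP 2.4.5.1, Generalities: "All the reported AE will be considered as treatment emergent adverse event (TEAE". It has no condition on onset date or worsening. The AE, SAE and AESI tables of number and percentage of patients are built on this set. Their denominator is the safety population, which SAP 2.3.1 defines as everyone who signed consent.

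The protocol brings earlier events into the TOPAZ database:

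- Section 10.1.1 lists two Visit 1 tasks: "Collection of AEs still ongoing at the end of the Extension Study CAMMS03409" and "Collection of the AE that occurred between the final visit of the CAMMS03409 study and Visit 1".
- Section 10.4.2 repeats this in its reporting rules ("At Visit 1 the ongoing AEs started during the Extension Study CAMMS03409", together with gap events). It adds that AEs and AESIs still open at the close of a patient's "participation in CAMMS03409 should be followed during the LPS13649 study".
- Footnote a to Table 2 foresees the serious and special-interest cases ("If an SAE or an AESI ongoing from the CAMMS study is reported in TOPAZ study") and waives one supplementary form for them.
- The gap before Visit 1 may last 3 months, or 6 months in the US (Protocol 10.1.1 and Appendix D; SAP 2.5.3).

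One protocol section points the other way. Section 10.4.1.4 sets a category apart: "Medical conditions present at the initial trial visit (Visit1) that do not worsen in severity or frequency during the trial". These count as baseline conditions and not as AEs.

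Onset is available for analysis. Protocol 10.4.2 states: "The Study Investigator should specify the date of onset".

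**The concern.** Safety is the primary endpoint (SAP 2.1.4), and the protocol defines it largely as incidence. In this long-term follow-up the reader most wants to know whether new events, autoimmune ones above all, still appear late after treatment. Protocol 11.4.2 promises particular attention to the development of autoimmune disorders. A table row that counts a thyroid disorder ongoing since CAMMS03409 together with one first seen in TOPAZ does not answer that question.

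The mixing can also conceal events. Under the once-per-patient rule in SAP 2.4.5.1, a carried-over event can take the place of a new occurrence of the same event in the same patient. The first-event-only rule can do the same in the AESI table by number of courses.

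The same TEAE, SAE and AESI results feed the yearly reports in SAP section 3. Gap events weigh most there, because follow-up is still short.

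**Working it through.** The plan states no figure on this point, so there is none to reproduce. The check has two parts: whether any other text supplies the missing condition, and how large the effect could be.

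**1. Does another text supply an onset condition?**

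| Text | What it does | Does it cure the gap? |
|---|---|---|
| SAP 2.1.4, observation period | Starts at the screening visit; defines the death periods | No. SAP 2.4.5.1 refers to it only when explaining table sorting |
| SAP 2.1.4.1, recording from consent | Says when AE recording starts | No. Protocol 10.1.1 and 10.4.2 expressly add earlier events |
| SAP 2.4.5, TOPAZ data only | Filters by the study in which data were collected | No. Carried-over and gap events are collected in TOPAZ |
| SAP 2.5.2, partial onset dates | Assumes that pre-treatment events are not treatment-emergent | No. It covers missing or partial dates only and relies on a TEAE period that the SAP never defines |
| Protocol 10.4.1.4 | Stable conditions at Visit 1 are not AEs | In part. It conflicts with 10.1.1, 10.4.2 and Table 2 footnote a, and does not cover gap events that resolved before Visit 1 |

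**2. What do the percentages then measure?** They are not new incidence in TOPAZ, because earlier events are included. They are not cumulative incidence since first alemtuzumab, because SAP 2.4.5 leaves out events that resolved during CAMMS03409.

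**3. Scale of a table row.** The input is up to 1248 patients (Clinical Trial Summary). Added percentage points = patients whose only event in the row is an earlier one / 1248.

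- 12/1248 = 0.96%; 12.48/1248 = 1.0%
- 62/1248 = 4.97%
- 125/1248 = 10.02%

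**4. Illustration for one row, on assumed rates.** Let c be the share of patients with the event carried over and i the new-onset share among the rest. The table shows c + (1 − c)i; the new-onset percentage is (1 − c)i.

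| c | i | Table shows | New onset |
|---|---|---|---|
| 0% | 5% | 5.0% | 5.0% |
| 2% | 5% | 6.9% | 4.9% |
| 10% | 5% | 14.5% | 4.5% |
| 20% | 5% | 24.0% | 4.0% |

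**5. Illustration for gap events alone.** Assume a constant AE rate, the longest permitted gap for every patient, and full follow-up to the stated time. Gap share of counted events = gap / (gap + follow-up).

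- At 12 months: 3/15 = 20.0%; US 6/18 = 33.3%
- At 60 months: 3/63 = 4.8%; US 6/66 = 9.1%
- With Visit 1 on the day of the last CAMMS03409 visit: 0%

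These are shares of events. They do not convert directly into percentages of patients.

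**The case against.** The strongest defence is that everyone here has a treatment history. The objective is long-term safety of alemtuzumab, and a gap event or a late CAMMS03409 event will usually follow first exposure, so calling it treatment-emergent is a conservative convention. That would support a cumulative count since first alemtuzumab. It does not support this one, which leaves out earlier events that had resolved.

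A second defence reads Protocol 10.1.1 and 10.4.2 as collection rules and 10.4.1.4 as the counting rule. That reading is possible for ordinary AEs. It is harder to hold for SAEs and AESIs, given Table 2 footnote a, and it does not reach gap events that resolved before Visit 1. Sites may therefore differ in what they carry over.

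Several limits stand:

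- The analysis is descriptive, with no systematic testing (SAP 2.4.5).
- The SAE, discontinuation and AESI listings show onset dates, so cases can be separated one by one. No planned summary table does this.
- IARs, the infusion-day AESI table, on-study deaths, and laboratory or vital-sign change summaries are little affected.
- The gap illustration is an upper case, since Visit 1 should coincide with the last CAMMS03409 visit where possible. Later enrolees also have less than 60 months of follow-up.
- Protocol 6.3 and 11.5 plan a yearly partial database lock and no interim analysis, whereas SAP section 3 plans yearly interim analyses. The point about yearly results applies to whatever is produced from those locks.

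**Conclusion.** The concern holds. Followed as written, the plan builds its primary safety tables from a set that can contain events with onset before TOPAZ, and no text in either document removes them. The gap in the definition is certain; its numerical effect is not. The documents give no count of carried-over or gap events. The effect is zero if sites leave out every stable condition under Protocol 10.4.1.4 and there are no gap events, and it grows with the share carried over. It is likely to matter most for chronic AESIs with low new onset. The scale is about 1 percentage point per 12 to 13 affected patients, assuming the maximum enrolment of 1248. This should be fixed. The descriptive analysis and the onset dates in the listings keep it from being more serious.

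**What to change.** In SAP 2.4.5.1:

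- Flag each AE by onset. Base the TOPAZ AE, SAE and AESI incidence tables on events with onset on or after consent/V01, or ongoing at V01 and worsening afterwards.
- Apply the once-per-patient and first-event rules after the flag.
- Tabulate carried-over CAMMS03409 events and gap events separately, so that nothing is lost.
- Use the same flag for the numerators of the SAE and AESI rates, with person-time over the matching period.

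Define the TEAE period and align the partial-date rule in SAP 2.5.2 with it. Reconcile Protocol 10.4.1.4 with 10.1.1 and 10.4.2.

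The cost is one derived flag, a few added tables, SAP wording in two sections and a protocol clarification. Onset dates are already collected. The worsening part needs a check of how the eCRF records it, because Protocol 10.4.2 asks for onset and intensity but names no worsening date.

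Percentages will fall or stay the same. Rates may move either way. If the denominator is already TOPAZ time, they fall or stay the same. If total treatment exposure means the person-years in SAP 2.4.3.1, which run from first prior-study treatment, the nominal durations in SAP 1.4 give 2 + 4 + 5 = 11 years against 5, taking the extension at its minimum of 4. Matching the denominator to TOPAZ then multiplies the rate by 11/5 = 2.2 before any events are removed, so rates rise unless more than 1 − 5/11 = 54.5% of counted events drop out.
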